8.2.3 Safety Lead-in

A continuous monitoring rule for safety will be instituted, to guard against excess toxicity from pre-operative treatment with ruxolitinib at the FDA-indicated starting dose for patients with myelofibrosis (20 mg bid for patients with a platelet count \geq 200,000 or 15 mg bid for patients with a platelet count \geq 150,000 and < 200,000). The first cohort of 6 patients will be treated at this starting dose. After enrollment of the 6th patient, we will continuously monitor the number of

Phase 2 - Ruxolitinib Page 49 of 67

patients who discontinue ruxolitinib and come off study for ruxolitinib-attributable toxicity. A qualifying toxicity must be at least possibly related to ruxolitinib, as judged by the treating investigator, and fulfill one of the following definitions:

- Grade ≥ 3 non-hematologic toxicity, with the exception of asymptomatic electrolyte abnormalities manageable with repletion.
- Intolerable non-hematologic toxicities of any grade, which persist despite optimal medical management.
- Grade ≥ 3 thrombocytopenia or neutropenia.

If the posterior probability of \geq 33% toxicity rate exceeds 50% for patients having to discontinue window treatment due to qualifying toxicity, this would be considered unacceptable and would result in de-escalating the starting dose of ruxolitinib to 10 mg p.o. bid, the FDA-indicated starting dose in polycythemia vera, for all subsequent patients. This would be the starting dose in all patients with a qualifying platelet count for this study (\geq 150,000), including those with platelet count \geq 150,000 and < 200,000 and those with platelet count > 200,000. (see section 5.2 Dose De-Escalation Rule)

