Based on clinical experience to date in myelofibrosis, the following adverse effects may be associated with ruxolitinib: thrombocytopenia, anemia, neutropenia, bruising dizziness, headache, urinary tract infection, weight gain, flatulence, and herpes zoster. Thrombocytopenia, anemia, and neutropenia are dose-related effects, which occur at a median of 8 weeks after initiation of ruxolitinib, and in studies of longer duration have been generally treated by withholding ruxolitinib. Occasionally patients with anemia may require a transfusion. Patients taking ruxolitinib may be at risk for infection and should be monitored for this. The incidence of clinically significant hematologic toxicity is expected to be very low in the current study population, due to the short ruxolitinib exposure, as well as the absence of a primary bone marrow malignancy predisposing to hematologic toxicity.

Some people who take ruxolitinib have developed certain types of non-melanoma skin cancers.

Availability

All tablets are oval and white with "INCY" on one side and "25" on the other. Additional information regarding ruxolitinib can be found in the package insert.

Storage and handling

Phase 2 - Ruxolitinib Page 29 of 67

In addition to the active ingredient, each ruxolitinib tablet contains microcrystalline cellulose, lactose monohydrate, magnesium stearate, colloidal silicone dioxide, sodium starch glycolate, povidone, and hydroxypropyl cellulose. Ruxolitinib will be supplied as 5 mg tablets in bottles containing 60 tablets each. Labels contain, at a minimum, the following information: product name, tablet strength, batch number, directions for use, storage conditions, and appropriate caution statements. Ruxolitinib tablets should be stored in a secure area at 25°C (77°F); excursions permitted between 15°-30°C (59°-86°F).

Side Effects

Complete and updated adverse event information is available in the Investigational Drug Brochure and/or product package insert.

4.2 **Drug Accountability**

The Investigational Pharmacist will manage drug accountability records. Damaged supplies will be destroyed at the study site and adequate records of the damaged supplies will be kept at the site. Study investigators will be responsible for drug accountability.

4.3 **Drug Ordering**

Ruxolitinib will be supplied by Incyte Pharmaceuticals.

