5.2 Dose De-escalation Rule

A continuous monitoring rule for safety will be instituted, to guard against excess toxicity from pre-operative treatment with ruxolitinib at the FDA-indicated starting dose for patients with myelofibrosis (20 mg bid for patients with a platelet count \geq 200,000 or 15 mg bid for patients with a platelet count \geq 150,000 and < 200,000). See section 8.3.3 Safety Lead-In

Table 5.2 below describes the number of toxicity events per number of treated patients required to trigger the ruxolitinib de-escalation rule. Table 8 also shows the posterior probability that the rate exceeds 33%, and the binomial probability associated with the decision for an assumed

Phase 2 - Ruxolitinib Page 30 of 67

33% discontinuation rate. The prior probability has a beta distributions with parameters a = 1 and b = 9, assumes a 10% mean with an approximate 80% mid-range of .0 to .22.

Table 5.2 Boundaries for the De-Escalation Rule

Participants	Treatment-Related Discontinuations	PP(π > 33%)*	$Pr(X \ge r p = .33)$
6	5	.629	.017
8	6	.685	.019
11	7	.673	.037
14	8	.664	.054
17	9	.657	.071
20	10	.650	.087
23	11	.645	.101
27	12	.594	.145
30	13	.592	.156
33	14	.590	.167

 $^{^*\}pi$ is the discontinuation rate. The minimum acceptable upper bound of a treatment-related discontinuation is 33%. PP(π > 33%) is the posterior probability that the discontinuation rate exceeds this 33% upper bound. This posterior probability of discontinuation is calculated from the prior distribution, the number of participants treated and the observed number of treatment-related discontinuations.

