7.6 Adverse Events Monitoring

All adverse events, whether or not unexpected, and whether or not considered to be associated with the use of the study drug, will be entered into OnCore[®], as noted above.

The Investigator will assess all adverse events and determine reportability requirements to the UCSF Data and Safety Monitoring Committee (DSMC) and UCSF's Institutional Review Board, the Institutional Review Board (IRB); and, when the study is conducted under an Investigational New Drug Application (IND), to the Food and Drug Administration (FDA) if it meets the FDA reporting criteria.

All adverse events entered into OnCore® will be reviewed by the Helen Diller Family Comprehensive Cancer Center Site Committee on a weekly basis. The Site Committee will review and discuss at each weekly meeting the selected toxicity, the toxicity grade, and the attribution of relationship of the adverse event to the administration of the study drug(s).

All grade(s) 3-5 adverse events entered into OnCore® will be reviewed on a monthly basis at the Site Committee meetings. The Site Committee will review and discuss the selected toxicity, the toxicity grade, and the attribution of relationship of the adverse event to the administration of the study drug(s).

In addition, all suspected adverse reactions considered "serious" entered into OnCore®, will be reviewed and monitored by the Data and Safety Monitoring Committee on an ongoing basis and discussed at DSMC meetings, which take place every six weeks.

Phase 2 - Ruxolitinib Page 47 of 67

Protocol CC# 16201

For a detailed description of the Data and Safety Monitoring Plan for a Multicenter Phase 2 or 3 Institutional Study at the Helen Diller Comprehensive Cancer Center please refer Appendix 2.

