The UCSF Coordinating Center provides administration, data management, and organizational support for the participating sites in the conduct of a multicenter clinical trial. The UCSF Coordinating Center will also coordinate monthly conference calls with the participating sites to communicate the review of adverse events, safety data, and other study matters.

The Principal Investigator at the UCSF Coordinating Center will hold the role of Study Chair. The Study Chair is responsible for the overall conduct of the study and for monitoring its safety and progress at all participating sites. The Study Chair will conduct continuous review of data and patient safety and discuss each patient's treatment at monthly UCSF Site Committee meetings. The discussions are documented in the UCSF Site Committee meeting minutes.

Multicenter communication

The UCSF Coordinating Center provides administration, data management, and organizational support for the participating sites in the conduct of a multicenter clinical trial. The UCSF Coordinating Center will also coordinate monthly conference calls with the participating sites. The following issues will be discussed as appropriate:

- Enrollment information.
- Adverse Events (i.e., new adverse events and updates on unresolved adverse events and new safety information).
- Protocol Violations.
- Other issues affecting the conduct of the study.

Adverse events reporting to the DSMC will include reports from both the UCSF Coordinating Center, as well as the participating sites. The DSMC will be responsible for monitoring all data entered in OnCore® and eFlorence (a FDA 21 CFR part 11-compliant electronic data repository) at the UCSF Coordinating Center and the participating sites as per the study-specific guidelines. The data (i.e., copies of source documents) from the participating sites will

Phase 2 - Ruxolitinib Page 60 of 67

be downloaded into the PC console of OnCore or from eFlorence prior to the monitoring visits in order for the DSMC to monitor the participating site's compliance with the protocol and FDA regulations.

3. Review and Oversight Requirements

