3.3 Review of Adverse Event Rates

If an increase in the frequency of Grade 3 or 4 adverse events (above the rate reported in the Investigator Brochure or package insert) is noted in the study, the Study Chair at the UCSF Coordinating Center is responsible for notifying the DSMC at the time the increased rate is identified. The report will indicate if the incidence of adverse events observed in the study is above the range stated in the Investigator Brochure or package insert.

Phase 2 - Ruxolitinib Page 62 of 67

If at any time the Study Chair stops enrollment or stops the study due to safety issues, the DSMC Chair and DSMC Director must be notified within 1 business day and the IRB must be notified within 10 business days via an iRIS Reporting Form.

Data and Safety Monitoring Committee Contacts:

[name]

UCSF HDFCCC

[name]

DSMC Monitors

UCSF HDFCCC

[name]

Revision #3 (12Nov2017)

Approved by NCI (09Feb2012)

Phase 2 - Ruxolitinib Page 63 of 67

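### Low-priority improvement: the 8.2.3 de-escalation criterion can already be met at 4 of 4 or 5 of 5 patients, but the rule does not start until the 6th is enrolled

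*Combined protocol and SAP*

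**What the plan says.** Section 8.2.3 sets the lead-in: "The first cohort of 6 patients will be treated at this starting dose". Monitoring for de-escalation follows: "After enrollment of the 6th patient, we will continuously monitor the number of" patients who come off ruxolitinib for qualifying toxicity. The action criterion is a posterior probability, for a rate of at least "33% toxicity rate exceeds 50% for patients having to discontinue window treatment due to qualifying toxicity, this would be considered unacceptable". The consequence is a 10 mg bid starting dose for every later patient.

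Section 5.2 supplies the prior: "The prior probability has a beta distributions with parameters a = 1", with b = 9 and mean 10%. The note to Table 5.2 says the posterior is calculated from participants treated and discontinuations observed. The first row of the table is 6 participants with 5 discontinuations (posterior .629, binomial tail .017). No boundary is given for fewer than six.

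Other safeguards run from the first patient:
- Section 5.5 stops drug in a patient with qualifying toxicity.
- Section 7.6 provides Site Committee review: "The Site Committee will review and discuss at each weekly meeting the selected toxicity, the toxicity grade", together with attribution.
- Appendix 2, section 2 adds: "The Study Chair will conduct continuous review of data and patient safety".
- Appendix 2, section 3.3 requires the Study Chair to notify the DSMC if grade 3 or 4 events run above the brochure or package-insert rate. It also contemplates a halt: "If at any time the Study Chair stops enrollment or stops the study due to safety issues".

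The plan expects little trouble in so short a window. Section 4.1.1 says "The incidence of clinically significant hematologic toxicity is expected to be very low in the current study population".

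**The concern.** The plan defines an unacceptable dose by a posterior probability but attaches no consequence to that definition until the sixth patient is enrolled. If the first four patients all stop for ruxolitinib toxicity, the definition is met. The written rule still starts patients 5 and 6 at 20 or 15 mg bid. If both tolerate it, the count is 4 of 6, the posterior falls below the threshold, and the rule does not act at that point either. Similarly, five stops in five patients would still leave patient 6 starting at the higher dose.

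At stake are one or more further patients awaiting curative surgery who would start at a dose the plan's own criterion already calls unacceptable.

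**Working it through.** **Inputs.** Prior Beta(1,9), bound .33 and the ten tabulated rows (5.2 and Table 5.2); threshold .50 and first look at patient 6 (8.2.3); 45 patients (3.2).

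**Formula.** With r discontinuations in n treated, the posterior is Beta(1 + r, 9 + n − r), and PP = Pr(rate > .33).

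**The plan's own figures.** For 5 of 6 the posterior is Beta(6,10), PP = .629, and Pr(X ≥ 5 | 6, .33) = .017. Both match. All ten rows of Table 5.2 reproduce in both columns. A bound of 1/3 gives .618 in the first row, so .33 is the value the plan used.

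**The same criterion before patient 6.**

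| Stops / treated | Posterior | PP | Above .50? |
|---|---|---|---|
| 1/1 | Beta(2,9) | .108 | no |
| 2/2 | Beta(3,9) | .241 | no |
| 3/3 | Beta(4,9) | .403 | no |
| 4/4 | Beta(5,9) | .562 | yes |
| 4/5 | Beta(5,10) | .486 | no |
| 5/5 | Beta(6,9) | .699 | yes |
| 4/6 | Beta(5,11) | .415 | no |
| 5/6 | Beta(6,10) | .629 | yes |

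The 4 of 4 result does not depend on rounding the bound: with 1/3 it is .552. Binomial tails for the two new boundaries are .33⁴ = .012 and .33⁵ = .004.

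**Gain.** This is an exact binomial recursion over patients 1 to 45. The only difference between versions is whether the first look is at patient 6 or patient 1. Each outcome is taken as known before the next patient starts.

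| True rate | Acts by patient 4 (written / changed) | Acts by patient 6 (written / changed) | Expected starts at 20 or 15 mg (written / changed) | Fewer |
|---|---|---|---|---|
| 33% | 0 / .012 | .017 / .022 | 35.72 / 35.63 | 0.09 |
| 40% | 0 / .026 | .041 / .050 | 26.78 / 26.66 | 0.13 |
| 50% | 0 / .063 | .109 / .125 | 16.21 / 16.02 | 0.19 |
| 60% | 0 / .130 | .233 / .254 | 10.76 / 10.44 | 0.32 |
| 70% | 0 / .240 | .420 / .442 | 8.14 / 7.62 | 0.52 |

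Check: the gain equals Pr(4/4) times the further starts the written rule would allow after 4/4. At 33%, .0119 × 7.88 = .09; at 50%, .0625 × 3.09 = .19; at 70%, .2401 × 2.18 = .52.

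Under the plan's prior, Pr(4/4) = B(5,9)/B(1,9) = .0014. The gain averaged over Beta(1,9) is about 0.013 starts out of 45; at a true rate of 10% it is 0.003.

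**Cost.** Extra probability of ever de-escalating by patient 45 is .00007, .0006, .0010 and .0010 at true rates of 10%, 20%, 25% and 33%. On a 1% grid up to 33%, the maximum is .0011, at 29%.

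**Lag (assumption).** If 45 patients enroll over the roughly 12 months in 8.2.4, accrual is 45/12 = 3.75 a month, or one start about every 8 days. With 14 to 21 days of dosing, about two patients are on drug at once. Counting participants treated, 4 of 4 then requires all four to stop before patient 5's first dose; after that, four stops are 4 of 5 and do not trigger. A fifth stop before patient 6 starts gives 5 of 5, so that boundary can be reached without 4 of 4 ever being seen. If instead only resolved patients are counted and the written rule may act as soon as the sixth is enrolled, the gain can be 0.

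**The case against.** The strongest reply is that nothing here is broken. Sections 5.2 and 8.2.3 agree, the run-in is stated openly, and a minimum cohort before a Bayesian rule acts is a legitimate choice. The figures give a reason for one: a single tolerating patient after 4 of 4 brings the posterior back to .486. After 4 of 4, the written rule would never fire by patient 45 with probability .70 at a true rate of 10%, and .085 at 33%. The prior also makes rates where the gain is visible unlikely: Pr(rate > 33%) = .027 and Pr(rate > 50%) = .002. All of this stands, and it is why the point is low priority.

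A reader might infer that patients 1 to 5 have no group-level protection. The documents do not support that. The weekly review, the Study Chair's continuous review, the duty to notify the DSMC and the power to stop enrollment have no six-patient wait. The notification duty even has an external benchmark. Four consecutive toxicity stops would be unlikely to pass unexamined. What none of these does is set the next patient's starting dose; only the 8.2.3 rule does that by a fixed criterion.

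The objection does not show that the run-in is needed to prevent overreaction. The prior carries the weight of ten patients at a 10% mean, so 1 of 1, 2 of 2 and 3 of 3 cannot trigger, and the added chance of de-escalating at acceptable rates is about .001.

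**Conclusion.** The point holds as a minor, inexpensive improvement. The plan's own criterion is met at 4 of 4 and 5 of 5, before the written rule can act. Applying it from the first patient would avoid at most 0.09 to 0.52 starts at 20 or 15 mg out of 45 at true rates of 33% to 70%. These are upper limits, because they assume each outcome is known before the next start and that the Study Chair does not step in first.

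It would be tempting to call the lead-in an error, or the rule invalid. Neither follows: 5 of 6 is a correct trigger, the table reproduces, and operation from patient 6 onward is unaffected. The prior is a disclosed choice and is not in question here. The documents do not say how many patients have been treated; if six or more have, the change has no effect.

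**What to change.** Keep the prior, the 33% bound, the 50% threshold and the 10 mg bid consequence. Make three edits:

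1. In 8.2.3, apply the existing criterion from the first treated patient.
2. In the same section, treat the first six at the starting dose *unless the criterion is met earlier*.
3. In Table 5.2, add two rows: 4 participants, 4 discontinuations (.562, binomial .012); and 5 participants, 5 discontinuations (.699, binomial .004). Add a note that 4 of 5 (.486) does not trigger. The 5 of 5 row is needed because patients overlap. It also prevents the 4 of 4 row from being carried forward to five patients.

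No new visit, test, committee or patient is required. Under 9.4 the change needs PRC and IRB approval and an update to the participating sites, so it should be included in the next amendment and not prompt one of its own. The statistical cost is at most about .001 extra de-escalation at true rates up to 33%, plus accepting a 4 of 4 trigger that one tolerating patient would have reversed.

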- If participants experience any grade 3-4 ruxolitinib-related non-hematologic toxicities in the neo-adjuvant window, the study drug will be discontinued and they will be removed from the study. (Exception: Patients with asymptomatic grade 3 electrolyte abnormalities manageable with repletion) Patients may also be removed from study for intolerable non-hematologic toxicities of any grade, which persist despite optimal medical management.
- If participants experience grade ≥ 3 thrombocytopenia or neutropenia, ruxolitinib will be discontinued and they will be removed from the study.
- Grade 3 anemia does not require discontinuation from protocol. Patients may be transfused per discretion of the treating physicians.
- For mild or moderate (grade 1 or 2) side effects that are difficult to tolerate, treatment
 may be held for up to 1 week. Treatment may be resumed at the same dose, if there is
 improvement by at least one grade. Dose delays more than 1 week will not be permitted.
 If treatment is restarted, study physicians should aim for at least 3 days of ruxolitinib
 exposure prior to planned surgery.

In two Phase 3 clinical studies of ruxolitinib in myelofibrosis, the median time to onset of first CTCAE grade two or higher anemia was 6 weeks, and approximately 8 weeks until onset of grade 3 or 4 thrombocytopenia. In nearly all cases, ruxolitinib-induced anemia and thrombocytopenia could be reversed with dose reduction or interruption; occasionally red blood cell or platelet transfusions were required. Thus, given the short 2-3 weeks of treatment during this study, it is expected that few, if any, participants will develop hematologic abnormalities. Moreover, participants in the current study do not have a primary bone marrow malignancy which is the target of ruxolitinib and thus predisposes to hematologic toxicity. Any participants that experience anemia or thrombocytopenia may be transfused if deemed necessary by the treating physician.

Although clinically significant hematologic and non-hematologic toxicity is unexpected during the 14-21 days of protocol treatment in patients with operable HNSCC, a continuous monitoring rule for excess toxicity will be instituted. Please see Section 5.6 below.

5.6 **Monitoring and Toxicity Management**

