Each patient receiving ruxolitinib will be evaluable for safety. The safety parameters include all laboratory tests and hematological abnormalities, physical findings, and spontaneous reports of adverse events reported to the investigator by patients.

Each patient will be assessed periodically for the development of any toxicity as outlined in Section 6 Study Procedures and Observations. Toxicity will be assessed according to the NCI

Phase 2 - Ruxolitinib Page 32 of 67

CTCAE v4.0. Dose adjustments will be made according to the system showing the greatest degree of toxicity.

We will monitor for the following anticipated adverse events:

Anemia

In the two Phase 3 clinical studies, median time to onset of first CTCAE Grade 2 or higher anemia was approximately 6 weeks. One patient (0.3%) discontinued treatment because of anemia. In patients receiving ruxolitinib, mean decreases in hemoglobin reached a nadir of approximately 1.5 to 2.0 g/dL below baseline after 8 to 12 weeks of therapy and then gradually recovered to reach a new steady state that was approximately 1.0 g/dL below baseline. This pattern was observed in patients regardless of whether they had received transfusions during therapy.

In the randomized, placebo-controlled study, 60% of patients treated with Jakafi and 38% of patients receiving placebo received red blood cell transfusions during randomized treatment. Among transfused patients, the median number of units transfused per month was 1.2 in patients treated with ruxolitinib and 1.7 in placebo treated patients.

Thrombocytopenia

In the two Phase 3 clinical studies, in patients who developed Grade 3 or 4 thrombocytopenia, the median time to onset was approximately 8 weeks. Thrombocytopenia was generally reversible with dose reduction or dose interruption. The median time to recovery of platelet counts above 50 X 10⁹/L was 14 days. Platelet transfusions were administered to 4.7% of patients receiving ruxolitinib and to 4.0% of patients receiving control regimens. Discontinuation of treatment because of thrombocytopenia occurred in 0.7% of patients receiving ruxolitinib and 0.9% of patients receiving control regimens. Patients with a platelet count of 100 X 10⁹/L to 200 X 10⁹/L before starting ruxolitinib had a higher frequency of Grade 3 or 4 thrombocytopenia compared to patients with a platelet count greater than 200 X 10⁹/L (16.5% versus 7.2%).

Neutropenia

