In the two Phase 3 clinical studies, 1.0% of patients reduced or stopped ruxolitinib because of neutropenia.

Table 5.6 provides the frequency and severity of clinical hematology abnormalities reported for patients receiving treatment with Jakafi or placebo in the placebo-controlled study.

Table 5.6 Worst Hematology Laboratory Abnormalities in the Placebo-controlled Studya

	Jal	kafi (N=155)		Placebo (N=151)			
Laboratory Parameter	All Grades ^b (%)	Grade 3 (%)	Grade 4 (%)	All Grades (%)	Grade 3 (%)	Grade 4 (%)	
Thrombocytopenia	69.7	9.0	3.9	30.5	1.3	0	
Anemia	96.1	34.2	11.0	86.8	15.9	3.3	
Neutropenia	18.7	5.2	1.9	4.0	0.7	1.3	

a Presented values are worst Grade values regardless of baseline

Phase 2 - Ruxolitinib Page 33 of 67

b National Cancer Institute Common Terminology Criteria for Adverse Events, version 3.0

Additional Data from the Placebo-controlled Study

25.2% of patients treated with ruxolitinib and 7.3% of patients treated with placebo developed newly occurring or worsening Grade 1 abnormalities in alanine transaminase (ALT). The incidence of greater than or equal to Grade 2 elevations was 1.9% for ruxolitinib with 1.3% Grade 3 and no Grade 4 ALT elevations.

17.4% of patients treated with ruxolitinib and 6.0% of patients treated with placebo developed newly occurring or worsening Grade 1 abnormalities in aspartate transaminase (AST). The incidence of Grade 2 AST elevations was 0.6% for ruxolitinib with no Grade 3 or 4 AST elevations.

16.8% of patients treated with ruxolitinib and 0.7% of patients treated with placebo developed newly occurring or worsening Grade 1 elevations in cholesterol. The incidence of Grade 2 cholesterol elevations was 0.6% for ruxolitinib with no Grade 3 or 4 cholesterol elevations.

6 Study Procedures and Observations

The study-specific procedures and assessments are outlined in the Study Calendar – Section 6.1

Screening assessments must be performed within 28 days prior to the first dose of investigational product. Any results falling outside of the reference ranges may be repeated at the discretion of the investigator.

All on-study visit procedures are allowed **a window of ±5 days** unless otherwise noted. Treatment or visit delays for public holidays or weather conditions do not constitute a protocol violation.

Phase 2 - Ruxolitinib Page 34 of 67

6.1 **Study Calendar**

Table 6.1 Schedule of Study Procedures and Assessments

Study Procedures	Screening	Treatment Period			Surgery		Final study

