		Days 1 thru 14 to 21	Days 22 thru 28 (if surgery is delayed)	Pre-surgery visit (within 5 days prior to surgery)	(between 14-28 days of ruxolitinib start) ⁹	4-week post-op visit	visit (12-week post- op)
Informed Consent	Х						
History and Physical Examination ^a	x			X		х	x
Vital Signs, Weight	Х			X		Х	X
ECOG-PS	Х			X		Х	Х
Pregnancy Test ^b	Х						
EKG ^c	Х						
Clinical Blood Testsd	Х			X		Х	Х
Cross-sectional imaging studye	х			Х			
Research Blood Collection ^h	х			Х			
Ruxolitinib ^f		х	Х	X (take until morning of surgery)			
Surgery ^g					Х		
Tumor sample ⁱ	Х				Х		
Archival tissue collection	Х						

a. History and physical examination within 8 weeks prior to study entry. This should include surgical assessment of the primary tumor, including fiberoptic nasopharyngoscopy or examination under anesthesia as indicated per standard of care, and as determined by the treating surgeon. Patients will be reevaluated within 5 days prior to scheduled surgery. Toxicity and compliance as evidenced by pill count and patient diaries will be assessed.

Phase 2 - Ruxolitinib Page 35 of 67

b. Pre-menopausal women of childbearing potential (WOCBP) must have a negative urine or serum pregnancy test within 4 weeks of registration. A negative pregnancy test must then be documented within 72 hours of Day 1 of ruxolitinib treatment.

c. The standard of care EKG performed for pre-surgical evaluation should be used. EKGs performed within 12 weeks prior to study entry may be substituted, provided the patient has experienced no interval cardiac event.

- d. Clinical blood tests include CBC with differential (to include total white blood cell count, absolute neutrophil count, hemoglobin, hematocrit and platelets), serum chemistries (to include sodium, potassium, chloride, HCO₃, BUN, creatinine, glucose, magnesium and calcium), liver function tests (to include total bilirubin, AST, ALT, total protein, albumin and alkaline phosphatase), coagulation studies (PT/INR and PTT), and C-reactive protein (CRP). Clinical blood tests will be repeated once within 5 days prior to surgery, and at the 4-week and 12-week post-operative visits if clinically indicated according to the investigator.

 Coagulation studies are not required at the 4 week or 12 week post-surgical visits.

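### Patients whose surgery is delayed can dose for up to 12 days before resection with no scheduled toxicity review or blood count; a smaller point is that the de-escalation count is worded two ways

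*Combined protocol and SAP*

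**What the plan says.** **Monitoring before surgery.** The calendar in 6.1 has one on-treatment safety column, headed "Pre-surgery visit (within 5 days prior to surgery"). Footnote d says "Clinical blood tests will be repeated once within 5 days prior to surgery". Footnote a, which covers the clinical re-evaluation with its toxicity and compliance review, ties the same 5 days to scheduled surgery. Section 6.3.2.2 asks sites to aim for the day before or the day of surgery and allows 5 days for logistics.

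**Delay.** Footnote g allows surgery to slip by up to 7 days; footnote f lets dosing continue to surgery, to a maximum of 28 days, with the last dose on the morning of resection. For a delayed patient, 6.3.2.2 continues the drug and waives repetition of the history and physical, the blood tests and the imaging. The calendar column for days 22 to 28 lists ruxolitinib only.

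**Stopping and counting.** For grade 3 or worse thrombocytopenia or neutropenia, section 5.5 says "ruxolitinib will be discontinued and they will be removed from the study". The de-escalation rule in 8.2.3 monitors "patients who discontinue ruxolitinib and come off study for ruxolitinib-attributable toxicity". The Table 5.2 column is headed as treatment-related discontinuations, and its footnote says that π "is the discontinuation rate. The minimum acceptable upper bound of a treatment-related discontinuation is 33"%. The sentence introducing that table in 5.2 instead describes "the number of toxicity events per number of treated patients required" to trigger the rule.

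**The concern.** The delay matters most. A patient still taking a drug with dose-related cytopenias could reach a major resection with protocol blood counts and a toxicity review up to 12 days old. The section 5.5 stopping rule for cytopenias depends on a measured count, and 6.3.2.2 waives the measurement. The trial also enrols patients with platelets from 150,000 to below 200,000. In the myelofibrosis studies cited in 5.6, grade 3 or 4 thrombocytopenia was more frequent with a baseline of 100 to 200 x 10^9/L than above 200 (16.5% versus 7.2%).

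The count matters less, but it sets the starting dose for all later patients, so it should have one reading. The only scheduled on-treatment check is steered towards the day before or the day of surgery, when the drug is about to end anyway. A qualifying toxicity found with no dose left, or in a result returned after the last dose, is a toxicity event but arguably not a discontinuation.

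**Working it through.** **1. The delay interval.** Inputs: check window 5 days (6.1, 6.3.2.2); maximum delay 7 days (footnote g); dosing to the morning of surgery (footnote f).

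Days from check to actual surgery = days from check to planned surgery + delay.

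- Check 5 days before the planned date, full delay: 5 + 7 = 12 days.
- Check on the planned surgery day, full delay: 0 + 7 = 7 days.
- No delay: 0 to 5 days.

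Worst-case examples: planned day 14, check day 9, surgery day 21, 21 - 9 = 12; planned day 21, check day 16, surgery day 28, 28 - 16 = 12. As a share of dosing this is 12/21 = 57% and 12/28 = 43%.

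**2. The texts side by side for a delayed patient.**

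| Item | Calendar (6.1) | 6.3.2.2 after a delay |
|---|---|---|
| Blood tests | within 5 days of surgery (column header, footnote d) | need not be repeated |
| Toxicity review | header: within 5 days of surgery; footnote a: of scheduled surgery | need not be repeated |

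The conflict is clear for the blood tests and only partial for the toxicity review.

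**3. Table 5.2 reproduced.** Prior Beta(1, 9), limit 0.33, trigger when the posterior probability exceeds 0.50. After r counted events in n patients the posterior is Beta(1 + r, 9 + n - r).

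- 5 of 6: Beta(6, 10), P(π > 0.33) = .629, as printed; 4 of 6 gives .415, no trigger.
- 14 of 33: Beta(15, 28), .590, as printed; 13 of 33 gives .460, no trigger.

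All ten rows match on both the posterior and the binomial column. The boundaries are sound; the only question is what enters r.

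**4. Where the two readings differ.** While doses remain, 5.5 converts a qualifying grade 3 or worse toxicity into a discontinuation, so both readings count it. They part only when the toxicity is found with no dose left or in a late-returned result. That is mainly silent thrombocytopenia or neutropenia, since symptomatic toxicity can surface earlier.

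**5. Possible size of the count point.** Table 5.6 (myelofibrosis, worst grade) gives grade 3-4 thrombocytopenia 9.0 + 3.9 = 12.9% and neutropenia 5.2 + 1.9 = 7.1%. Combined, this is 12.9% with full overlap to 20.0% with none. Checking the rule after every patient from the 6th to the 45th, the exact probability of triggering is .0017 at 12.9% and .025 at 20%, even if every such event is counted.

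Illustration with assumed rates: 5% silent cytopenia on top of other toxicity that is always counted. Probability of triggering with the cytopenias all counted versus none counted:

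| Other toxicity | By patient 33 | By patient 45 |
|---|---|---|
| 10% | .0040 vs .0004 | .0041 vs .0004 |
| 20% | .084 vs .023 | .099 vs .025 |
| 30% | .412 vs .215 | .504 vs .264 |

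The two figures in each cell are extremes; any true effect lies between them.

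**The case against.** **On the delay.** Twelve days needs both the earliest permitted check and the full delay, although 6.3.2.2 asks for the check on the day before or the day of surgery. The calendar schedules no safety visit between day 1 and the pre-surgery visit for anyone, so a patient planned for day 21 already goes 15 to 20 days to the first check (day 16 to day 21). The protocol defends light monitoring by late onset: for grade 3 or 4 thrombocytopenia, "the median time to onset was approximately 8 weeks" in the Phase 3 studies. Repeat tests are not forbidden, and a surgical team may order them. All of this stands and limits the size of the point. It does not explain why a count required within 5 days of surgery may be older when surgery moves and dosing has lengthened.

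**On the count.** Discontinuation is a legitimate tolerability measure. Section 8.2.3, its trigger sentence, and the Table 5.2 header and footnote all use it; one introductory phrase departs from it. A patient who takes the last planned dose did not have to discontinue, and the 10% prior mean and 33% limit are stated for discontinuations. This largely stands. What remains is that a toxicity meeting an 8.2.3 definition can be classified either way by an accident of timing.

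**Readings that go too far.**

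- A reader might infer that the de-escalation rule misses laboratory toxicity in general. It does not: a check 1 to 5 days before surgery still leaves doses to stop. Outside the rule, grade 3 and above events are recorded with attribution (7.4), and Appendix 2 requires review and notification of the DSMC if grade 3 or 4 rates exceed those in the Investigator Brochure or package insert.
- A reader might take .504 versus .264 as the loss in sensitivity. It rests on assumed rates, with other toxicity at three times the prior mean and no silent cytopenia counted.
- A reader might put the gap at 19 days (check on day 9, surgery on day 28). Footnote g's 7-day limit rules that out.

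**Conclusion.** The delay point holds as a patient-safety improvement. Under 6.3.2.2 a delayed patient may go 7 to 12 dosing days before surgery without a scheduled check after a full 7-day delay, against at most 5 days without delay. The 12-day figure is a worst case, and its frequency cannot be obtained from the documents. The inconsistency with the calendar is clear for the blood tests and partial for the toxicity review.

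The count point is a minor clarification. Table 5.2 is numerically correct. Only toxicities found when no dose is left are affected; their number is not derivable, and the expected effect on the rule is small. The cytopenia rates used for scale come from myelofibrosis patients with a median exposure of 9.5 months in the Phase 3 studies, against 2 to 4 weeks here, so they probably overstate what this trial would see.

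Neither point invalidates a planned analysis or shows that the dose rule fails.

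**What to change.** 1. **Section 6.3.2.2.** Amend the no-repeat notes so that a patient who keeps dosing after a surgical delay repeats the toxicity review and the standard pre-operative blood tests within 5 days of actual surgery. Align calendar footnote a by referring to actual surgery. Imaging need not be repeated. Cost: one further review and blood draw, in delayed patients only.

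2. **Sections 5.2 and 8.2.3, and the Table 5.2 header and footnote.** Use one definition: every patient with a toxicity that meets an 8.2.3 definition, is at least possibly related to ruxolitinib, and is found from first dose through the pre-surgery check, including results of that draw returned after the last dose, whether or not the drug was stopped early. Keep the prior, the 33% limit, the boundaries and the doses. Do not extend counting past surgery, because that would bring in surgical complications. Cost: protocol wording. Grade 3 and above events are already entered with attribution. The monitored event becomes slightly broader than discontinuation, so the rule may fire slightly more often.
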